**Treatment Modification for MLN0128 (TAK-228)-Related Adverse Events**

Event	CTCAE. V4 Grade	Action to be Taken
		
not already done
 
 
▪ Monitor FPG at least weekly until FPG resolves to <math>\leq</math> Grade 1
 
▪ Then re-start MLN0128 (TAK-228) and <math>\downarrow</math>1 dose level
 
▪ Continue with anti-diabetic treatment
 
▪ Check FPG weekly for 8 weeks, then continue checking every 2 weeks
 
 
Second and Subsequent Occurrence:
 
 
• Maintain dose level of MLN0128 (TAK-228), re- check FPG within 24 hours. If grade worsens or improves then follow specific grade recommendations. If FPG remains at Grade 2: 
 
○ Omit dose of MLN0128 (TAK-228)
 
○ Initiate or intensify with appropriate anti-diabetic treatment
 
○ Monitor FPG at least twice weekly until FPG resolves to <math>\leq</math> Grade 1
 
○ Then re-start MLN0128 (TAK-228) and <math>\downarrow</math>1 dose level
 
○ Continue with anti-diabetic treatment
 
○ Check FPG at least weekly for 8 weeks, then continue checking at least every 2 weeks
 
 
 

	Grade 3	
Immediately omit MLN0128 (TAK-228), initiate or intensify medication with appropriate anti-diabetic treatment, re-check FPG within 24 hours. If grade worsens or improves then follow specific grade recommendations.
 
 
• If FPG remains at Grade 3: 
 
○ Administer intravenous hydration and intervention for electrolyte/ketoacidosis/hyperosmolar disturbances as clinically appropriate
 
○ Continue to omit dose of MLN0128 (TAK-228)
 
○ Monitor FPG at least twice weekly until FPG resolves to <math>\leq</math> Grade 1
 
○ If FPG resolves to <math>\leq</math> Grade 1 in 7 days or less, then re-start MLN0128 (TAK-228) at the same dose level
 
 
 
• If FPG remains greater than Grade 1 severity for
 

--	---------	--

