## 6. DOSING DELAYS/DOSE MODIFICATIONS

Toxicities will be graded using the NCI CTCAE Version 4.0 and dose modifications of the study drugs will be made for hematologic and other toxicities. Patients experiencing study drug related toxicities that require a delay in dosing for >21 days will be discontinued from further participation in this study. In the event that patients must have treatment delayed with a treatment cycle due to toxicities, those doses held during a cycle will not be made up.

Dose Level	MLN0128 (TAK-228) Dose
0	3 mg flat dose daily continuous
-1	2 mg flat dose daily continuous
-2	2 mg daily 5 days/ week
-3	1 mg 5 days/week
-4	Withdraw from study

Treatment Modification for MLN0128 (TAK-228)-Related Adverse Events		
Event	CTCAE. V4 Grade	Action to be Taken
QTc prolongation	≥ Grade 3 or > 60ms change from baseline on at least two separate ECGs	
First Occurrence:
 
 
• Omit MLN0128 (TAK-228) dose
 
• Perform an analysis of potassium and magnesium, and if below lower limit of normal, correct with supplements to within normal limits. Concomitant medication usage must be reviewed.
 
• Perform a repeat ECG within one hour of the first QTcF of 500 ms
 
• If QTcF remains > 500 ms, repeat ECG as clinically indicated, but at least once a day until the QTcF returns to < 480 ms. Seek cardiologist input
 
• Once QTcF prolongation has resolved, MLN0128 (TAK-228) may be restarted at a one lower dose level
 
 
Second Occurrence:
 
 
• Permanently discontinue patient from the study treatment
 

	Other Cardiac Events	Grade 1-2
	Grade 3	
Omit dose of MLN0128 (TAK-228) until resolved to ≤ Grade 1
 
 
• If resolved within 7 days, then resume at same dose level of MLN0128 (TAK-228).
 
• If resolved in >7 days, resume at ↓1 dose level of MLN0128 (TAK-228).
 
• If not resolved in 21 days, then discontinue patient from study treatment.
 

	Grade 4	Permanently discontinue patient from the study treatment
Treatment Modification for MLN0128 (TAK-228)-Related Adverse Events		
Event	CTCAE. V4 Grade	Action to be Taken
ENDOCRINE		

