Fasting Plasma Glucose (FPG) (2 hrs fasting)	Grade 1	
Maintain dose level of MLN0128 (TAK-228), check FPG every week
 
 
• Initiate or intensify with appropriate anti-diabetic treatment as per investigator's discretion
 
• Instruct patient to follow dietary guidelines according to local and/or institutional standards for management of diabetes mellitus (such as those provided by the American Diabetes Association) during the study
 
• Consider use of oral anti-hyperglycemic therapy such as metformin
 
 
Check FPG daily for 8 weeks, then continue checking at least every 1 week

Grade 2	
First Occurrence:
 
 
• If signs or symptoms of hyperglycemia (for example, mental status changes, excessive thirst, polyuria), omit dose of MLN0128 (TAK-228) immediately and manage as for Grade 3 hyperglycemia (below)
 
• If asymptomatic, maintain MLN0128 (TAK-228) dose and re-check FPG within 24 hours. If grade worsens or improves then follow specific grade recommendations: 
 
○ If FPG remains at Grade 2: 
 
▪ Maintain dose level of MLN0128 (TAK-228)
 
▪ Initiate or intensify with appropriate anti-diabetic treatment
 
▪ Instruct patient to follow dietary guidelines according to local and/or institutional standards for management of diabetes mellitus (such as those provided by the American Diabetes Association) during the study
 
▪ Consider use of oral anti-hyperglycemic therapy such as metformin
 
 
 
○ If FPG does not resolve to <math>\leq</math> Grade 1 within 7 days after initiation/intensifying anti-diabetic treatment: 
 
▪ Omit dose of MLN0128 (TAK-228) if
 
 
 
 
 

---------	--

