**Treatment Modification for MLN0128 (TAK-228)-Related Adverse Events**

Event	CTCAE. V4 Grade	Action to be Taken
		
more than 7 days, then discontinue patient from study treatment:
 
 
○ Initiate or continue anti-diabetic treatment as appropriate
 
○ Instruct patient to follow dietary guidelines according to local and/or institutional standards for management of diabetes mellitus (such as those provided by the American Diabetes Association) during the study
 
○ Consider use of oral anti-hyperglycemic therapy such as metformin
 
○ Check FPG at least weekly for 8 weeks, then continue checking at least every 2 weeks
 
 
For non-fasting plasma glucose >250-500mg/dL (> 13.9 – 27.8 mmol/L) accompanied by signs/symptoms of hyperglycemia (for example, mental status changes, excessive thirst, polyuria), or presence of blood or urine ketones, omit MLN0128 (TAK-228) and follow guidance for management of Grade 3 fasting plasma glucose (FPG).

	Grade 4	
Immediately omit dose of MLN0128 (TAK-228), initiate or intensify medication with appropriate anti-diabetic treatment, re-check within 24 hours, if confirmed Grade 4:
 

• Administer intravenous hydration and intervention for electrolyte/ketoacidosis/hyperosmolar disturbances as clinically appropriate

• Discontinue patient from the study. Instruct patient to follow dietary guidelines according to local and/or institutional standards for management of diabetes mellitus (such as those provided by the American Diabetes Association) during the study

• Consider use of oral anti-hyperglycemic therapy such as metformin

• Check FPG weekly for 8 weeks, then continue checking at least every 2 weeks if clinically indicated

--	---------	---

Treatment Modification for MLN0128 (TAK-228)-Related Adverse Events		
Event	CTCAE. V4 Grade	Action to be Taken
		For non-fasting plasma glucose >500 mg/dL (> 27.8 mmol/L) accompanied by signs/symptoms of hyperglycemia (for example, mental status changes, excessive thirst, polyuria), or presence of blood or urine ketones, discontinue MLN0128 (TAK-228) and following guidance for management of Grade 4 fasting plasma glucose (FPG).
GASTROINTESTINAL		
Mucositis oral	Grade 1	Maintain MLN0128 (TAK-228) dose level

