Event	CTCAE. V4 Grade	Action to be Taken
	Grade 4	Permanently discontinue patient from the study treatment
SKIN AND SUBCUTANEOUS TISSUE DISORDERS		
Rash (maculo-papular)	Grade 1	Maintain dose level of MLN0128 (TAK-228). Consider initiation appropriate skin toxicity therapy (such as antihistamines, topical corticosteroids)
	Grade 2	Maintain dose level of MLN0128 (TAK-228). Initiate/intensify appropriate skin toxicity therapy (such as antihistamines, topical corticosteroids)
	Grade 3	Omit dose of MLN0128 (TAK-228) until resolved to Grade $\leq 1$ , then: 
 
• If resolved in <math>\leq 7</math> days, maintain at same dose of MLN 0218
 
• If resolved in <math>> 7</math> days, resume at <math>\downarrow 1</math> dose level of MLN0128 (TAK-228)
 
• If not resolved in 21 days, then discontinue patient from study treatment.
 

	Grade 4	Patients who develop Grade 4 rash should permanently discontinue study treatment, unless they derive clinical benefit, in which case they may be retreated at a reduced dose level after recover to $\leq$ Grade 1 severity. Grade 4 rash is defined as rash acneiform/papulopustular with papules and/or pustules covering any % body surface area, which may or may not be associated with symptoms of pruritus or tenderness, and are associated with extensive superinfection with intravenous (IV) antibiotics indicated; life threatening consequences (NCI CTCAE Version 4.03, effective date 14 June 2010).
INVESTIGATIONS		
Cholesterol high and/or hypertriglyceridemia	Grade 1	Maintain MLN0128 (TAK-228) dose level
	Grade 2	Maintain dose if tolerable, if toxicity becomes intolerable, omit dose MLN0128 (TAK-228) until resolved to $\leq 1$ , then restart MLN0128 (TAK-228) as the same dose level
	Grade 3	Omit dose of MLN0128 (TAK-228) until resolved to Grade $\leq 1$ , then restart at $\downarrow 1$ dose level of MLN0128 (TAK-228)
	Grade 4	Permanently discontinue patient from the study treatment

OTHER ADVERSE EVENTS		
Other AEs	Grade 1-2	Maintain MLN0128 (TAK-228)

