	Grade 3	Omit dose of MLN0128 (TAK-228) until resolved to $\leq$ Grade 1, then: 
 
• If resolved in <math>\leq</math> 7 days, maintain at same dose of MLN 0218
 
• If resolved in <math>></math> 7 days, resume at <math>\downarrow</math>1 dose level of MLN0128 (TAK-228)
 
• If not resolved in 21 days, then discontinue patient from study treatment.
 

	Grade 4	Permanently discontinue patient from the study treatment
		Note: Omit dose for $\geq$ Grade 3 vomiting or Grade 3 nausea only if the vomiting or nausea

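### A symptomatic repeat Grade 2 glucose stays on drug until the re-check, although the same symptoms at a first Grade 2 stop it at once

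*Combined protocol and SAP*

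**What the plan says.** The relevant text is the FPG row of the Treatment Modification table in Section 6.

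- **First Grade 2 event.** The cell splits by symptoms. With symptoms: "If signs or symptoms of hyperglycemia (for example, mental status changes, excessive thirst, polyuria), omit dose of MLN0128 (TAK-228) immediately", after which the patient is managed as Grade 3. Without symptoms: "If asymptomatic, maintain MLN0128 (TAK-228) dose and re-check FPG within 24 hours".
- **Second or later Grade 2 event.** There is no split. Every patient is told: "Maintain dose level of MLN0128 (TAK-228), re- check FPG within 24 hours. If grade worsens or improves then follow specific grade recommendations". The hold, the twice-weekly monitoring and the restart one level lower all come after the re-check, and only if FPG is still Grade 2.
- **Grade 1.** This is where an improved re-check leads: "Maintain dose level of MLN0128 (TAK-228), check FPG every week".

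Other rules bear on the same patient:

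- The Grade 3 FPG row holds drug for symptoms with non-fasting glucose above 250 mg/dL, or for blood or urine ketones.
- The Other AEs row keeps drug going for Grade 1-2 events. At Grade 3 it says "Omit dose of MLN0128 (TAK-228) until resolved to" Grade 1 or below, and at Grade 4 it discontinues.
- Section 5.2 requires glucose-lowering treatment for every Grade 2 or higher reading (fasting above 160 mg/dL) and immediate contact with the site for a home reading of 150 mg/dL or more.
- Section 5.3 allows treatment to end for an unacceptable adverse event, or for a change in the patient's condition, in the investigator's judgment.

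**The concern.** The first-occurrence cell makes symptoms, including mental status changes, a reason to stop drug immediately at Grade 2. The repeat cell drops that reason without explanation. Read literally, a patient who has already had one Grade 2 event gets a weaker symptom rule at the next one, for the same grade and the same symptoms.

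The cell will be used in practice. Section 7.1.1 lists hyperglycemia among the likely events (above 20%), and Section 5.2 says most episodes have been Grade 1 or 2. What is at stake is a short avoidable exposure in a symptomatic patient. No efficacy result depends on it.

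**Working it through.** The plan states no figure on this point, so the check is a comparison of the cells followed by a count of doses.

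**1. The three Grade 2 paths (Section 6)**

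| | First, symptomatic | First, asymptomatic | Second or later, any patient |
|---|---|---|---|
| Before the re-check | hold | maintain | maintain |
| Still Grade 2 at the re-check | managed as Grade 3 | maintain; hold if not at Grade 1 or lower within 7 days of starting or stepping up glucose-lowering treatment | hold at once |
| Restart | same level if at Grade 1 or lower within 7 days | one level lower after a hold | one level lower after a hold |
| Discontinue | if above Grade 1 for more than 7 days | general 21-day limit | general 21-day limit |

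Only the first line makes the repeat cell less protective than the first event for a symptomatic patient awaiting the re-check. If the re-check reads Grade 1, the patient passes to the Grade 1 row, which maintains the dose, so the event may never lead to a hold.

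**2. What the other rules leave uncovered**

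Taking ketones as a trigger in their own right, the Grade 3 row covers any ketone-positive patient and any symptomatic patient with non-fasting glucose above 250 mg/dL. The Other AEs row covers Grade 3-4 symptoms. Section 5.2 requires treatment and site contact but states no hold. Section 5.3 permits stopping but does not require a hold. What remains is a ketone-negative repeat fasting Grade 2 with Grade 1-2 symptoms that does not meet the non-fasting rule.

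**3. Doses before the re-check, on-time dosing**

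Section 5.1 gives one dose daily at a fixed time. Let the reading fall t hours after the last dose (0 < t ≤ 24) and the re-check w hours after the reading (0 < w ≤ 24). The next dose is due at 24 hours and the one after at 48.

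- One dose is taken if t + w > 24; otherwise none.
- A second would need t + w > 48, which is impossible because t + w ≤ 24 + 24 = 48.

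A half-hourly grid of 48 × 48 = 2,304 combinations agrees: 1,128 give 0 doses, 1,176 give 1 and none gives 2. These counts show the possible range. They are not probabilities.

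**4. The late-dose edge case**

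Section 5.1 lets a missed dose be taken up to 12 hours late, provided consecutive doses are not within 12 hours of each other. Suppose the usual time is 08:00 and the dose is missed. FPG reads Grade 2 at 10:00, the late dose is taken at 11:00, the next dose at 08:00 (21 hours later, so allowed), and the re-check is at 09:30 (23.5 hours after the reading). Two doses fall before the re-check.

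**5. Size by dose level**

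| Level | Dose | On time (0 or 1 dose) | Edge case (2 doses) |
|---|---|---|---|
| 0 | 3 mg | 0 or 3 mg | 6 mg |
| -1 | 2 mg | 0 or 2 mg | 4 mg |
| -2 | 2 mg | 0 or 2 mg | 4 mg |
| -3 | 1 mg | 0 or 1 mg | 2 mg |

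Level -2 is "2 mg daily 5 days/ week" and level -3 is also dosed 5 days in 7, so a non-dosing day (2 of 7, or 29%) lowers the count. An immediate hold would make every entry zero.

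**The case against.** The best case against acting is that care is largely provided elsewhere. Home readings are taken before the dose, and contact with the site is required from 150 mg/dL, which is 160 − 150 = 10 mg/dL below the Grade 2 threshold. The site may therefore intervene before the next dose is swallowed. Glucose-lowering treatment is mandatory and does not wait for the re-check, and Section 5.2 reports a quick response to metformin. A sensible investigator may hold drug anyway.

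It can also be said that the repeat cell is a different scheme, not the first-occurrence scheme with a line missing. Compared with the first-occurrence symptomatic path it is stricter on restart (one level lower, against the same level if resolved within 7 days) and more lenient on discontinuation (no 7-day limit).

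All of this stands, and it keeps the point small. It does not remove it. None of these rules requires a hold for the patient described, and the cell written for that patient says to maintain the dose.

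A reader might go further and infer that the table is laxer at recurrence throughout. It is not: Grade 2 still present at the re-check is held at once in the repeat cell, whereas the first-occurrence asymptomatic path allows up to 7 days after treatment is started or stepped up.

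**Conclusion.** The gap is real and minor. It concerns a ketone-negative repeat fasting Grade 2 with Grade 1-2 symptoms, in the period of at most 24 hours before the re-check, and it amounts to 0 or 1 dose with on-time dosing or 2 in the late-dose edge case. This rests on a literal reading of the cell, on the re-check being done within its 24 hours, and on ketones alone being enough to trigger the Grade 3 row.

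The documents give no rate of repeat or symptomatic Grade 2 events, so the number of patients affected cannot be estimated. Two inferences should be resisted. The text does not show that symptomatic patients go untreated, because Section 5.2 requires treatment of every one of them. Nor does it suggest any bias in response rate, PFS or the decision rule, none of which depends on this cell.

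**What to change.** Rewrite the opening of the repeat-occurrence Grade 2 cell as two branches:

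- **Symptomatic:** stop MLN0128 immediately, start or step up glucose-lowering treatment, and repeat FPG within 24 hours. If FPG is then Grade 1 or lower and symptoms have resolved, resume under the Grade 1 row. If FPG is still Grade 2, keep holding and follow the cell's existing steps.
- **Asymptomatic:** maintain the dose and repeat FPG within 24 hours, as now.

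The explicit resumption rule is needed because the cell's twice-weekly monitoring and lower restart apply only when FPG is still Grade 2 at the re-check. Without it, a held patient who improves would have no stated path back. Requiring symptoms to have resolved also prevents the Grade 1 row from restarting drug on the glucose value alone. A worse reading still goes to the Grade 3 or 4 row. The rest of the cell and the 21-day limit stay as they are, and the 7-day discontinuation rule for Grade 3 is not brought in.

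The change is confined to one table cell, with no new visits, tests, patients or stopping rule. Its downside is an occasional held dose. It could help patients still on drug and the planned 40 − 20 = 20 extension patients (Schema and Section 13.2).

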**Treatment Modification for MLN0128 (TAK-228)-Related Adverse Events**

Event	CTCAE. V4 Grade	Action to be Taken
		
more than 7 days, then discontinue patient from study treatment:
 
 
○ Initiate or continue anti-diabetic treatment as appropriate
 
○ Instruct patient to follow dietary guidelines according to local and/or institutional standards for management of diabetes mellitus (such as those provided by the American Diabetes Association) during the study
 
○ Consider use of oral anti-hyperglycemic therapy such as metformin
 
○ Check FPG at least weekly for 8 weeks, then continue checking at least every 2 weeks
 
 
For non-fasting plasma glucose >250-500mg/dL (> 13.9 – 27.8 mmol/L) accompanied by signs/symptoms of hyperglycemia (for example, mental status changes, excessive thirst, polyuria), or presence of blood or urine ketones, omit MLN0128 (TAK-228) and follow guidance for management of Grade 3 fasting plasma glucose (FPG).

	Grade 4	
Immediately omit dose of MLN0128 (TAK-228), initiate or intensify medication with appropriate anti-diabetic treatment, re-check within 24 hours, if confirmed Grade 4:
 

• Administer intravenous hydration and intervention for electrolyte/ketoacidosis/hyperosmolar disturbances as clinically appropriate

• Discontinue patient from the study. Instruct patient to follow dietary guidelines according to local and/or institutional standards for management of diabetes mellitus (such as those provided by the American Diabetes Association) during the study

• Consider use of oral anti-hyperglycemic therapy such as metformin

• Check FPG weekly for 8 weeks, then continue checking at least every 2 weeks if clinically indicated

--	---------	---

Treatment Modification for MLN0128 (TAK-228)-Related Adverse Events		
Event	CTCAE. V4 Grade	Action to be Taken
		For non-fasting plasma glucose >500 mg/dL (> 27.8 mmol/L) accompanied by signs/symptoms of hyperglycemia (for example, mental status changes, excessive thirst, polyuria), or presence of blood or urine ketones, discontinue MLN0128 (TAK-228) and following guidance for management of Grade 4 fasting plasma glucose (FPG).
GASTROINTESTINAL		
Mucositis oral	Grade 1	Maintain MLN0128 (TAK-228) dose level
	Grade 2	Maintain MLN0128 (TAK-228) dose level if tolerable, if toxicity becomes intolerable omit dose of MLN0128 (TAK-228) until resolved to Grade $\leq$ 1, then restart at the same dose level
	Grade 3	Omit dose of MLN0128 (TAK-228) until resolved to Grade $\leq$ 1, then restart at $\downarrow$ 1 dose level of MLN0128 (TAK-228), If not resolved in 21 days, then discontinue patient from study treatment.
	Grade 4	Permanently discontinue patient from the study treatment
GENERAL DISORDERS		
Fatigue (asthenia)	Grade 1-2	Maintain MLN0128 (TAK-228) dose level
	Grade 3	Omit dose of MLN0128 (TAK-228) until resolved to $\leq$ Grade 1, then: 
 
• If resolved in <math>\leq</math> 7 days, maintain dose level of MLN0128 (TAK-228)
 
• If resolved in <math>></math> 7 days, <math>\downarrow</math> 1 dose level of MLN0128 (TAK-228)
 
• If not resolved in 21 days, then discontinue patient from study treatment.
 

	Grade 4	Patients who develop Grade 4 nonhematological toxicities (with the exception of isolated non-clinically significant laboratory values) should permanently discontinue study treatment, unless they derive clinical benefit, in which case they may be retreated at a reduced dose level after recovery to $\leq$ Grade 1 severity.
HEMATOLOGIC		
Neutropenia (ANC)	Grade 1-2	Maintain dose level of MLN0128 (TAK-228)

Grade 3	Omit dose of MLN0128 (TAK-228) until resolved to $\leq$ Grade 1 or baseline, then: 

• If resolved in <math>\leq 7</math> days, maintain dose level of MLN0128 (TAK-228)

• If resolved in <math>> 7</math> days, resume treatment at <math>\downarrow 1</math> dose level of MLN0128 (TAK-228)

• If not resolved in 21 days, then discontinue

---------	--

Treatment Modification for MLN0128 (TAK-228)-Related Adverse Events		
Event	CTCAE. V4 Grade	Action to be Taken
		patient from study treatment.
	Grade 4	Permanently discontinue patient from the study treatment
Febrile Neutropenia	Grade 3	Omit dose of MLN0128 (TAK-228) until resolved to Grade 1 or baseline, then: 
 
• If resolved in <math>\leq 7</math> days, resume treatment at <math>\downarrow 1</math> dose level of MLN0128 (TAK-228)
 
• If resolved in <math>> 7</math> days, discontinue MLN0128 (TAK-228)
 

Thrombocytopenia	Grade 1-2	Maintain dose level of MLN0128 (TAK-228)
	Grade 3	Omit dose of MLN0128 (TAK-228) until resolved to $\leq$ Grade 1 or baseline then: 
 
• If resolved in <math>\leq 7</math> days, resume treatment at <math>\downarrow 1</math> dose level of MLN0128 (TAK-228)
 
• If resolved in <math>> 7</math> days, discontinue MLN0128 (TAK-228)
 

	Grade 4	Permanently discontinue patient from the study treatment
HEPATIC		
Bilirubin	Grade 1	Maintain dose level of MLN0128 (TAK-228)
	Grade 2 (with ALT or AST grade 1 or 2)	Omit dose of MLN0128 (TAK-228) until resolved to $\leq$ Grade 1 or baseline, then resume at the same dose level of MLN0128 (TAK-228)
	Grade 3 (with ALT or AST grade 1 or 2)	Omit dose of MLN0128 (TAK-228) until resolved to $\leq$ Grade 1 or baseline, then: 
 
• If resolved in <math>\leq 7</math> days, maintain same dose level of MLN0128 (TAK-228)
 
• If resolved in <math>> 7</math> days but less than 21 days, resume treatment at <math>\downarrow 1</math> dose level of MLN0128 (TAK-228).
 
• If not resolved in 21 days, then discontinue patient from study treatment.
 

	Grade 4	Permanently discontinue patient from the study treatment

